8. STUDY PARAMETERS & SERIAL OBSERVATIONS

The patient will be evaluated at the time of enrollment. Quality of life and toxicity will be monitored weekly. The final assessment will occur on the day of surgery. No further surveillance will be performed for this trial.

8.1 Observations and Tests

The following observations and tests are to be performed and recorded:

	Baseline	Weekly	On the day of
	Daseille	Weekly	surgery
History & Physical Exam	Х		Х
Performance Status	Х		Х
WBC, Diff, Hgb, Hct, Platelets	Х		Х
Chemistries: Na, K, Cl, CO2,			
BUN, creatinine, glucose,	х		X
bilirubin(T/D), SGOT (AST),		^	
SGPT (ALT), Alk Phos,			
CA-125	Х		Х
2,6 DMBQ			1
Toxicity Assessment	2	2	2
Grade 1-4 AEs		2	2
QoL Survey	3	3	3
Cancer tissue for paraffin			Х
embedded and frozen			Α

- 1. drawn in a red top tube
- 2. National Cancer Institute's Common Toxicity Criteria CTC version 4
- 3. Quality of Life Survey (QoL) FACT-O

9. EVALUATION CRITERIA

The evaluation criteria for this study are primarily safety, toxicity, and QoL. Secondary assessments are disease response based on CA125, apoptosis and tumor proliferation, 2,6 DMBQ serum levels, and molecular changes as indicated below.

9.1 Safety, Toxicity and Quality of Life: will be assessed as reviewed in section 6.

9.2 Response Criteria

9.21 Evaluation of Biomarkers

Biomarker-based response involves assessing the patient's longitudinal CA125 values. The definition of CA125 response is based on the Gynecologic Cancer Intergroup (GCIG 2005) criteria. CA125 response will be determined and compared between FWGE and placebo treated groups

9.22 2.6-DMBQ determination

2,6 DMBQ serum presence will be determined in FWGE versus placebo-treated groups.

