4. PATIENT ELIGIBILITY

4.1 Inclusion Criteria

- 4.11 Women with suspected epithelial ovarian, fallopian tube or primary peritoneal carcinoma scheduled to undergo surgical exploration with no prior treatment for the cancer. Signs of ovarian cancer include, but are not limited to: an elevated CA125, a complex pelvic mass, ascites, and carcinomatosis. These signs are not necessary for suspicion or enrollment in this protocol.
- 4.12 Age > 18 years and competent to give informed consent
- 4.13 Patient must have a ECOG Performance sttus of 0, 1, or 2 and a life-expectancy of at least 60 days.
- 4.14. Patients must have adequate:
 - 4.141 Bone marrow function: Hemoglobin greater than or equal to 9gm/dl. Absolute neutrophil count (ANC) greater than or equal to 1,500/ul, equivalent to Common Toxicity Criteria (CTCAE v4.0) grade 1. Platelets greater than or equal to 100,000/ul.
 - 4.142 Renal function: creatinine less than or equal to 1.5 x institutional upper limit normal (ULN), CTCAE v4.0 grade 1.

- 4.143 Hepatic function: Bilirubin less than or equal to 1.5 x ULN (CTCAE v4.0 grade 1). SGOT and alkaline phosphatase less than or equal to 2.5 x ULN (CTCAE v4.0 grade 1).
- 4.15 Study subjects must sign an approved informed consent and authorization permitting release of personal health information.
- 4.16 Women of childbearing potential must have a negative serum pregnancy test prior to the study entry and be practicing an effective method of birth control during the course of the study, in a manner such that risk of failure is minimized. Prior to study enrollment, women of childbearing potential must be advised of the importance of avoiding pregnancy during trial participation and the potential risk factors for an intentional pregnancy.

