6.2 Treatment plan

- 6.21 All subjects will undergo:
 - 6.211 history and physical examination within 28 days of study entry.
 - 6.212 laboratory evaluation: complete blood count, differential, comprehensive metabolic panel and CA125 test prior to starting protocol therapy and preoperatively.
 - 6.213 serum pregnancy test (within 7 days of starting study drug), for women of child-bearing potential.
 - 6.214 Evaluation for National Cancer Institute's Common Toxicity Criteria, all grades at the time of enrollment, then weekly and the day of surgery.
 - 6.215 Quality of life questionnaire (FACT-O) at the time of enrollment, then weekly and the day of surgery (Appendix I).
- 6.22 Patients will be randomized to treatment with either FWGE or placebo and assigned a blinded treatment number corresponding to one of the two treatment groups. The pharmacy will label the appropriate blinded drug specifically for the patient. A daily supply of drug will be given to the patient from the study pharmacy. The amount will be determined by the time until the surgical procedure is scheduled. Neither patients nor treating physicians will be informed of patients "treated/control" status.

Participants will undergo their planned surgery within 4th week after entry into the study. However, if there are delays, patients can continue to take drug/placebo

for a time period no greater than 2 months. If surgery has not occurred after this 2-month period, the patient will be removed from the study.

Participants will take the study drug up until the day prior to surgery. A separate consent form will be obtained for the surgical procedure.

6.23 The primary tumor tissue obtained during the subject's surgery will be transferred to the pathology department for processing.

6.231 Formalin Fixation

Tissue will undergo formalin fixation then embedment in paraffin; tumor tissue will be stained using the H&E process and will be examined by light microscopy. The tumor will also be stained by immunohistochemical (IHC) stain for proliferation marker Ki-67 (Anti-Ki67 primary antibody, catalog number 790-2910, Ventana, Tucson, AZ, USA). The proliferation index will be calculated by percent of nuclear staining of the tumor for tumor tissue treated with FWGE versus placebo and the result will be compared. The reading pathologist will be blinded to the treatment group.

6.232 Fresh frozen

An additional specimen, approximately 30mg, will be flash frozen.

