6.233 RNA extraction and Affymetrix gene expression analysis
A total of 20 fresh frozen primary OVCA tissues (10 FWGE- and 10 placebo-treated) will be used for RNA extraction. Tissues (~30mg) will be submerged in lysis buffer. Tissues are then pulverized in BioPulverizer H tubes (Bio101) using a Mini-Beadbeater (Biospec Products). Tubes are spun briefly to pellet the garnet mixture and reduce foam. The lysates are then transferred to a new 1.5 ml tube using a syringe and 21 gauge needle, followed by passage through the needle 10 times to shear genomic DNA. Total RNA will be collected using the Qiagen RNeasy Mini kit according to the manufacturer's instructions. RNA quality will be checked on an Agilent Bioanalyzer to assess quality of RNA via the 28S:18S ribosomal RNAs.

Microarray analysis: 10 μ g of total RNA will be used to develop the targets for Affymetrix microarray analysis and probes will be prepared according to the manufacturer's instructions. Briefly, biotin-labeled cRNA is produced by in vitro transcription, fragmented, and hybridized to customized Human Affymetrix U133-Plus 2.0 gene chip arrays at 45° C for 16 hours and then washed and stained using the GeneChip Fluidics.

Method of statistical analysis: The expression value will be calculated and normalized using iterative rank-order normalization (IRON) [18]. IRON has been shown to perform better than both MAS5 and RMA and is not model based like RMA. Batch effects will be checked by using PCA; if present, they will be removed using COMBAT [19]. The 54,675 probesets will be screened to remove control probesets, probesets with a small variance, and probesets expressed at low levels.

6.24 Blood will be drawn at the time of surgery and sent for CA125 and a red top tube will be drawn and sent to the laboratory for 2,6, DMBQ testing

6.25 2,6-DMBQ determination

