12.0 STATISTICAL CONSIDERATIONS

12.1 Study Design: This study is a randomized, double-blind, placebo-controlled, trial of the effect of FWGE on women with epithelial ovarian cancer scheduled to undergo surgery. As noted above, we recognize that the sample size in the current study will prohibit definitive statistical conclusions to be drawn on our primary objective (to test the safety and tolerability of FWGE), or our secondary objectives (to compare levels of FWGE active product, CA125 levels, proliferation, and gene expression in OVCAs from subjects receiving FWGE versus placebo). The study is neither designed nor powered to develop statistically significant results, rather, we seek to develop preliminary/pilot data that will enable us to pursue a future large phase II, peer-reviewed grant-funded

trial of adjuvant FWGE in women undergoing therapy for ovarian cancer. Preliminary data developed in the current proposal will support such grant applications.

- 12.2 Primary outcome variable: The principal parameters to be collected, analyzed and reported will be:
- patient and disease characteristics: age, race, co-morbidities, cancer histologic
 type and stage. Optimal versus suboptimal surgical cytoreduction.
 - differences in toxicity
 - differences in quality of life

For each measure, Student's t-test will be used to identify differences between FWGE-versus placebo-treated OVCAs.

- 12.3 Secondary outcome variables for placebo versus FWGE:
- -the presence of 2,6-dimethoxy-p-benzoquinone in the serum
- -the change in the tumor marker CA125,
- -tumor proliferation as measured by Ki-67.

For each measure, Student's t-test will be used to identify differences between FWGEversus placebo-treated OVCAs.

12.4 Secondary outcome variables for genomic changes in ovarian cancer tissue for placebo versus FWGE.

Expression values will be calculated using the robust multi-array average (RMA) algorithm implemented in the Bioconductor (http://www.bioconductor.org) extensions to the R statistical programming environment.

Student's t-test will be used to identify differentially expressed genes in comparisons between FWGE- versus placebo-treated genomic data. Differentially expressed genes will analyzed using GeneGO MetaCore™ software to identify represented biologic pathways.

12.5 Accrual, Sample Size, and Study Duration: The study plan is a one-stage, randomized, double-blind, clinical trial. Patients will be randomized with equal

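### Section 9.21 compares a CA125 response that the protocol never defines operationally and section 12.3 never analyses, on one post-baseline value per woman that no later sample can verify

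*Combined protocol and SAP*

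**What the plan says.** Section 9.21 describes the data basis as follows: "Biomarker-based response involves assessing the patient's longitudinal CA125 values". It then gives the rule, "The definition of CA125 response is based on the Gynecologic Cancer Intergroup (GCIG 2005) criteria", and its use: "CA125 response will be determined and compared between FWGE and placebo treated groups". The opening paragraph of section 9 likewise lists CA125-based disease response among the secondary assessments. The content of the criteria appears nowhere in the protocol.

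Section 12.3 lists the secondary outcome variables for the arm comparison. For CA125 it names "the change in the tumor marker CA125" and assigns Student's t-test. It does not mention response. Objective 2.221 asks only for pilot data on the impact of FWGE on CA125.

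On sampling, section 6.212 requires a "CA125 test prior to starting protocol therapy and preoperatively", and section 6.24 adds: "Blood will be drawn at the time of surgery and sent for CA125". Schema footnote a and the table in section 8.1 both place CA125 at two times, baseline and the day of surgery, with no weekly draw. Section 8 makes the day of surgery the final assessment and states: "No further surveillance will be performed for this trial".

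On entry, section 4.11 lists an elevated CA125 among the signs of ovarian cancer and then says: "These signs are not necessary for suspicion or enrollment in this protocol".

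**The concern.** The same secondary outcome is a category in one section and a continuous change in another, and only the change has an analysis. Whoever analyses the trial must therefore decide, after the data are in, what counts as a response, which women can be assessed for it, and how to compare it.

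The schedule does not help. A fall at the only post-baseline draw stands alone, with no repeat value to show whether it is sustained. Because women may enter without a raised CA125, the protocol also leaves open whether such women count as non-responders or as not evaluable.

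The protocol intends its pilot data to support grant applications for a larger phase II trial. A response rate labelled with a published criterion would carry weight there. If the label was applied without what the criterion requires, or if the schedule itself prevented confirmation, the rate would misinform that use.

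**Working it through.** **The plan's own figure.** Section 12.5 expects fewer than 10% of 20 women to be lost: 20 × (1 − 0.10) = 18 evaluable. This reproduces. No alpha, power or effect size is given, so no power calculation applies.

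**Count of CA125 values per woman** (schema footnote a, sections 6.212 and 6.24, table in 8.1):

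- Baseline 1 + weekly 0 + day of surgery 1 = 2 values.
- Post-baseline: 2 − 1 = 1.
- Available to verify a fall seen at that draw: 2 − 2 = 0.

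The count is the same whether surgery takes place at the planned 4 weeks or at the 2-month limit, because the second draw is tied to surgery and not to elapsed time. Sections 6.212 and 6.24 could be read as two separate preoperative draws, but the schema and the table show one. The protocol sets no spacing between two such draws and schedules nothing after surgery.

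**The two definitions side by side.**

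| | Section 9.21 | Section 12.3 |
|---|---|---|
| Outcome | Response category | Change |
| Rule written in the protocol | None; criteria cited by name | Change, scale not stated |
| Test | None | Student's t-test |
| Who is assessable | Not stated | Not stated |
| Values needed | Not stated | Two, as scheduled |

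**What the schedule allows, by case.** The protocol does not show whether the cited criteria need a confirming sample, so both cases are set out.

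- Confirmation required, at any interval longer than zero days: confirmed responses obtainable = 0 in each arm, since no sample follows the only post-baseline one.
- Confirmation not required: a response can be assigned from the two values. The schedule does not fix the number at zero, but no assigned response can be verified.

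**The denominator.** The documents do not give the share of women with a raised CA125 at entry. Assume 50% to 100%.

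- Raised at baseline: 18 × 0.5 = 9 up to 18 × 1.0 = 18 women, that is 9 / 2 = 4.5 to 18 / 2 = 9 per arm.
- With r responders, all of them among women with a raised baseline, the overall rate is r/18 if women with a normal baseline count as non-responders, and between r/18 and r/9 if they are not evaluable.
- At the 50% end the two conventions differ by a factor of 18 / 9 = 2. At 100% they agree.

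So over the assumed range, an unstated convention alone could double the reported rate.

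**The case against.** The strongest reply is that the CA125 objective is already served. Objective 2.221 does not mention response, section 12.3 names the change and a test for it, and two values are enough to estimate it. The study is a pilot that repeatedly disclaims definitive conclusions, and CA125 is a secondary measure. Two time points in one woman can also fairly be called longitudinal, and the words used in 9.21 leave room to adapt the cited criteria. All of this stands. It limits the point to a wording conflict with modest consequences, but it does not remove the conflict: 9.21 still promises a comparison that has no written rule, no denominator and no test.

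A reader might go further and infer that none of the 20 women can be a responder. The documents do not support this. It depends on a confirmation requirement that the protocol does not reproduce and that cannot be checked here. Varying the length of an assumed interval does not cover the case in which there is no such requirement.

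A reader might also infer that every woman with a normal baseline is bound to be counted as a non-responder. That too goes beyond the text: she might instead be not evaluable, and 9.21 does not say which.

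**Conclusion.** The point holds in limited form. From the documents alone, 9.21 and 12.3 name different CA125 outcomes, the response category has neither a written rule nor an analysis, each woman has one post-baseline value that no later sample can verify, and the response denominator is undefined. Only if the cited criteria require a confirming sample does it follow that no confirmed response is possible in either arm; that condition is an assumption. The possible twofold difference in the rate rests on the further assumption that only half of the evaluable women start with a raised value.

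It would be wrong to conclude that the CA125 objective cannot be met. The change from baseline to surgery remains estimable. The matter is worth settling before analysis because the correction needs no new data, but it does not threaten the trial's primary purpose.

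**What to change.** In section 9.21, and in the matching wording at the start of section 9, replace the response comparison with the section 12.3 measure as the single CA125 outcome, and state that no CA125 response rate will be reported.

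In section 12.3, specify the analysis: compare log day-of-surgery CA125 between arms, adjusted for log baseline CA125, in all randomised women with both values. The arm effect, back-transformed, is a ratio of day-of-surgery CA125 between FWGE and placebo at equal baseline. It uses only values already scheduled.

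Results in women with confirmed cancer and a raised baseline may be shown as supportive. They should not be required as the main comparison. Histology is learned after randomisation, and under the 50% assumption the raised-baseline condition alone would leave about 4 or 5 women per arm.

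The cost is a wording change in sections 9, 9.21 and 12.3, with no extra samples and no change in sample size. The downside is that there is no CA125 response rate to quote in later applications.

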9.23 Proliferation

Immunohistochemistry detection of Ki-67 will be carried out in OVCA obtained from women following treatment with FWGE or placebo. The percentage of positively stained cells relative to total cells in each section will be determined and compared between treatment groups.

10. DURATION OF STUDY

Duration of the intervention, including treatment and surgery will be completed within 4 weeks after beginning of study. If a patient's surgery is delayed, the maximum time a patient will be on this study is 2 months.

11. STUDY MONITORING & REPORTING PROCEDURES

11.1 Definition of Adverse Events (AE)

An adverse event is the development of an untoward medical occurrence, undesirable medical condition, or recurrence or deterioration of a pre-existing medical condition subsequent to exposure to FWGE. The adverse reaction must be reported to Moffitt Cancer Center IRB. This study will utilize the Common Terminology Criteria for Adverse Events version 4.0 (CTCAE v4.0) for toxicity and adverse event reporting. A copy of the CTCAE v 4.0 can be downloaded from the CTEP home page http://ctep.cancer.gov/reporting/ctc.html

11.2 Definition of Serious Adverse Events (SAE)

A serious adverse event is any untoward medical occurrence that:

- Results in death,
- Is life-threatening (defined as an event in which the patient was at risk of death at the time of the events; it does not refer to an event which hypothetically might have caused death if it were more severe),
- Requires inpatient hospitalization or causes prolongation of existing hospitalization.
- Results in persistent or significant disability/incapacity,
- Overdose

All grade 4 and 5 adverse events are by definition serious, and must be reported within 24 hours of being aware of the event, with follow-up reporting of outcome. Grade 2 or 3 adverse events that require or prolong hospitalization, that result in persistent or significant disability, or that are events that jeopardize the patient and require intervention to avoid their becoming fatal, life-threatening, or disabling are also serious and must be reported as soon as the investigator becomes aware of the event.

Collection of complete information concerning grade 3-4 SAEs is extremely important. Full description of each event will be followed. Thus, follow-up information which becomes available as the SAE evolves, as well as supporting documentation (e.g., hospital discharge summaries and autopsy reports), should be collected subsequently, if not available at the time of the initial reports, and within 24 hours sent using the same procedures as the initial SAE reports.

12.0 STATISTICAL CONSIDERATIONS

12.1 Study Design: This study is a randomized, double-blind, placebo-controlled, trial of the effect of FWGE on women with epithelial ovarian cancer scheduled to undergo surgery. As noted above, we recognize that the sample size in the current study will prohibit definitive statistical conclusions to be drawn on our primary objective (to test the safety and tolerability of FWGE), or our secondary objectives (to compare levels of FWGE active product, CA125 levels, proliferation, and gene expression in OVCAs from subjects receiving FWGE versus placebo). The study is neither designed nor powered to develop statistically significant results, rather, we seek to develop preliminary/pilot data that will enable us to pursue a future large phase II, peer-reviewed grant-funded

trial of adjuvant FWGE in women undergoing therapy for ovarian cancer. Preliminary data developed in the current proposal will support such grant applications.

- 12.2 Primary outcome variable: The principal parameters to be collected, analyzed and reported will be:
- patient and disease characteristics: age, race, co-morbidities, cancer histologic
 type and stage. Optimal versus suboptimal surgical cytoreduction.
 - differences in toxicity
 - differences in quality of life

For each measure, Student's t-test will be used to identify differences between FWGE-versus placebo-treated OVCAs.

- 12.3 Secondary outcome variables for placebo versus FWGE:
- -the presence of 2,6-dimethoxy-p-benzoquinone in the serum
- -the change in the tumor marker CA125,
- -tumor proliferation as measured by Ki-67.

For each measure, Student's t-test will be used to identify differences between FWGEversus placebo-treated OVCAs.

12.4 Secondary outcome variables for genomic changes in ovarian cancer tissue for placebo versus FWGE.

Expression values will be calculated using the robust multi-array average (RMA) algorithm implemented in the Bioconductor (http://www.bioconductor.org) extensions to the R statistical programming environment.

Student's t-test will be used to identify differentially expressed genes in comparisons between FWGE- versus placebo-treated genomic data. Differentially expressed genes will analyzed using GeneGO MetaCore™ software to identify represented biologic pathways.

12.5 Accrual, Sample Size, and Study Duration: The study plan is a one-stage, randomized, double-blind, clinical trial. Patients will be randomized with equal

probability to receive either FWGE or placebo. The study will accrue 20 patients. It is anticipated that the accrual of this many patients will be achieved in 18 months. Less than 10% of the patients registered are expected to be lost due to follow-up or any other reason, so 20 accruals should allow for 18 evaluable cases.

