3.5 Rationale for the Dosage Used in this Study

The dose of FWGE that has been chosen for the study, is the dose used in each of the three previous clinical trials. This consists of 5.5 grams of FWGE formulated as a water-soluble granulate with added 0.03 grams of stevia sweetener and orange flavorings (taking it to approximately 5.53 grams), dissolved in 150 mL of water, orally once-daily.

This dose has been tolerated well in previous clinical trials with no grade 3 or 4 toxicity, even when combined with chemotherapy.

With regard to length of the intervention, most patients are scheduled for surgery within 4 week interval. We do not want to delay a patient's surgery for the intervention.

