5. STUDY MODALITIES

5.1 FWGE

- 5.11 Formulation: American BioSciences Inc, who is the exclusive manufacturer of FWGE in the Unites States, produces fermented wheat germ extract. See Letter of Support (Appendix II). It is formulated as a granulate. One package contains 5.53 grams of FWGE combined with natural orange flavor and stevia Reb-A sweetener to create an instant drink mix. See compositional analysis (Appendix III).
- 5.12 Administration: FWGE is dissolved in 150ml water and taken orally daily.
- 5.13 Adverse effects

The clinical safety experience of FWGE is derived from trials in which FWGE has been used as a single agent or in combination with chemotherapeutic agents. FWGE has not been associated with any grade 3 or 4 toxicities

- 5.14 Storage: FWGE is to be maintained at <80 degrees F
- 5.15 Quality assurance of the manufacturing of FWGE in the U.S.
 - 5.151 The purchased wheat germ and yeast, which are the raw materials of FWGE production, are certified for human consumption. The origin of the wheat germ and yeast, used in the fermentation, are all U.S. certified.

- 5.152 After each batch of FWGE has been freeze-dried, it is tested for hazardous contaminates, such as toxic elements, including heavy metals, and for toxic microorganisms, such as E.Coli, Listeria, etc. Once, the lyophilizate has been found free from toxic contaminants, and has been qualified as microbiologically safe (such as complete lack of toxic micriorganisms, etc.), it is standardized to ensure batch-to-batch chemical compositional homogeneity and biological efficacy-related reproducibility.

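### Sections 12.2 and 12.3 assign one t-test to nominal, binary and repeated graded measures, which leaves the primary toxicity outcome without a per-patient definition, a test that works at zero events, or an interval

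*Combined protocol and SAP*

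**What the plan says.** Section 12.2 (primary outcome variables) lists "patient and disease characteristics: age, race, co-morbidities", histologic type, stage and cytoreduction status, then differences in toxicity and in quality of life. Section 12.3 lists "the presence of 2,6-dimethoxy-p-benzoquinone in the serum", "the change in the tumor marker CA125" and Ki-67. Each list closes with the sentence that begins "For each measure, Student's t-test will be used to identify differences between" and goes on to name the two arms.

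Toxicity is graded by CTC at enrollment, weekly and on the day of surgery (6.214 and the table in 8.1). Section 9.1 only refers back to section 6, and no section reduces these grades to one value per patient.

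The form of the 2,6-DMBQ endpoint varies. It is presence in 9.22 and 12.3. Section 12.1 states the aim as "to compare levels of FWGE active product", 3.4 also speaks of levels, and section 9 lists "apoptosis and tumor proliferation, 2,6 DMBQ serum levels, and molecular changes as indicated below". The assay in 6.25 returns a concentration. No cut-off for presence and no rule for values below the assay limit is given.

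On earlier experience, 3.5 says the dose was "tolerated well in previous clinical trials with no grade 3 or 4 toxicity", and 5.13 says "FWGE has not been associated with any grade 3 or 4 toxicities".

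For quality of life, 6.26 prescribes a paired t-test, whereas 12.2 prescribes Student's t-test between arms.

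**The concern.** A two-sample t-test compares means of one numerical value per patient. Several listed items do not have that form. Race and histologic type have no mean. Toxicity has several grades per patient and no stated summary, so the analyst would have to invent the primary toxicity variable after the fact. 2,6-DMBQ presence is yes/no.

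The trial's stated purpose is preliminary data for a phase II grant. For safety, that means event rates with an honest statement of what a small sample can exclude. If a toxicity category has no events in either arm, the prescribed test returns nothing, and the plan offers nothing else. A reader could then take no events as evidence of no risk, although 10 patients per arm cannot support that.

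**Working it through.** **Inputs from the documents.** 10 patients per arm (2.1, 3.4); 20 accrued, less than 10% lost, 18 evaluable (12.5). The plan's own figure reproduces: 20 × (1 − 0.10) = 18. No alpha, power or effect size is stated. I use a two-sided 5% level and 95% intervals, and equal arms of 10 or 9. True event rates and category counts below are assumptions.

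**1. The t-test at zero events.** For 0/1 data with observed proportion p, the sample variance is n·p(1 − p)/(n − 1). At 0/10 v 0/10 both variances are 0 and the difference is 0, so t = 0/0. The same holds at 0/9 v 0/9.

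**2. How likely this is.** P(no events in either arm) = (1 − p)^N. It depends only on the total N, so unequal arms do not change it.

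| Assumed true rate | N = 20 | N = 18 |
|---|---|---|
| 1% | 82% | 83% |
| 2% | 67% | 70% |
| 5% | 36% | 40% |
| 10% | 12% | 15% |
| 20% | 1% | 2% |

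This applies to one rare category, such as grade 3-4. For a common summary such as any toxicity it is negligible.

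**3. What an interval would show.** Clopper-Pearson upper limit at 0/n: 1 − 0.025^(1/n). For n = 10 this is 30.8%; for n = 9, 33.6%. Newcombe interval for the difference at 0/n v 0/n: ± z²/(n + z²) with z = 1.96. For n = 10, 3.84/13.84 gives ±27.8 points; for n = 9, 3.84/12.84 gives ±29.9 points.

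**4. 2,6-DMBQ analysed as presence.** At 10/10 v 0/10 both within-arm variances are 0, so t is infinite and carries no information on precision. The Newcombe interval for the 100-point difference is 60.8 to 100, with lower limit 1 − √(0.2775² + 0.2775²) = 0.608. If the endpoint is level, the t-test can be computed.

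**5. Nominal items with three or more categories.** Illustration with assumed counts 7/1/2 v 4/5/1 in three histologic types:

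| Codes | Mean difference | t-test p |
|---|---|---|
| 1, 2, 3 | 1.5 − 1.7 = −0.2 | 0.57 |
| 1, 3, 2 | 1.4 − 2.1 = −0.7 | 0.085 |
| 2, 1, 3 | 2.1 − 1.6 = +0.5 | 0.096 |

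The other three codings are mirror images. The result depends on labels with no meaning. For two-level items the p-value does not change with coding (6/10 v 3/10 gives 0.196 under every coding tried).

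**6. P-values on binary data.** Enumerating all outcomes under a common rate, counting 0/0 as no rejection, the maximum size of the nominal 5% t-test is 4.2% at 10 per arm and 5.7% at 9.

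**The case against.** The strongest reply is that this is a declared pilot, not powered for significance and not meant to support definitive conclusions; that the raw data are collected; and that a sensible analyst would tabulate race and histology and report 0/10 as it stands, from which any reader can derive the 30.8% limit. Much of this is fair, and it limits the consequence to analysis and reporting. It does not remove the fault. The disclaimer concerns power, and it neither defines the toxicity variable nor supplies a method for a sparse count. An analysis chosen after the data are seen is what a written plan should avoid.

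Several stronger readings are tempting but not supported:

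- A reader might infer that zero events or full separation leaves no estimate. The raw difference (0 or 100 points) exists; the test and its standard error fail.
- A reader might infer that the plan would publish a zero-width t interval. It prescribes a test and no interval; the gap is that no interval is planned.
- A reader might infer that the protocol predicts no grade 3-4 events. Sections 3.5 and 5.13 report earlier experience; 7.1 expects only good tolerability, and all grades are collected.
- A reader might infer that every categorical item depends on its codes. Only items with three or more unordered categories do. The counts above are assumed, none of those codings reaches p < 0.05, and these are mainly descriptive characteristics.
- A reader might infer that the 2,6-DMBQ analysis is unworkable. That holds only under full separation with presence as the endpoint.

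**Conclusion.** The point holds and should be fixed. Followed exactly, the rule in 12.2 cannot be applied to toxicity without inventing a per-patient variable. For a rare category it can return an undefined result: 36% of the time at an assumed true rate of 5% and 12% at 10%, with 20 patients. Nothing in the plan would then show that 0/10 is compatible with a rate up to 30.8% (33.6% for 0/9).

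The 2,6-DMBQ inconsistency between presence and level comes next, because the suitability of the t-test turns on it. Code dependence for race and histologic type is real but secondary. Distortion of p-values on binary data is modest and is not the reason for the change. The t-test itself is reasonable for age and Ki-67 percent.

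The probabilities rest on assumed event rates, since the documents give none for this population. The 0/0 result and the exact limits rest only on the arm size.

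**What to change.** 1. **Toxicity (12.2).** Define one summary per patient, for example the worst post-baseline grade above the enrollment grade. Report event rates by arm with exact 95% intervals and a Newcombe interval for the difference. Name any exact test in advance.
2. **Patient and disease characteristics (12.2).** Present a descriptive table by arm, not t-tested.
3. **2,6-DMBQ (12.3).** Reconcile 9.22 and 12.3 with 3.4, 6.25, 9 and 12.1. If presence, state the assay cut-off and give detection rates with exact intervals. If level, state how values below the limit are handled.
4. **Measures that suit the t-test.** Keep the two-sample t-test for Ki-67 percent. Keep it for FACT-O change only after one time point is named and 12.2 is reconciled with the paired t-test in 6.26.

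A log-ratio scale for CA125 change is optional and not part of this error.

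The cost is protocol wording and simple programming, with no new data, visits or patients. The downside is that exact tests can lose power at this size: for true rates of 50% v 10% with 10 per arm, the t-test has 47% power and Fisher's test about 30%. Estimates with intervals should therefore lead.
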